STUDY DESIGN	
Comparative, randomized, Single center, Open label study to compare the safety and efficacy of oral Ciprodiazole 500 mg (Ciprofloxacin /Metronidazole) versus currently used Ciprofloxacin Tablets & Metronidazole tablets in pelvi-abdominal infections and following IV antibiotics in post-operative period, for pelvi-abdominal surgeries or acute conditions
 
A study population of 312 patients who had pelvi-abdominal infection or started IV antibiotics for 48 hours, post-operative or till be able to tolerate oral intake in post-operative period, for pelvi-abdominal surgeries or acute conditions. They will be randomized by computer, to receive Ciprodiazole ® tablets (Ciprofloxacin/Metronidazole) versus currently used Ciprofloxacin Tablets & Metronidazole tablets for a duration not exceeding 15 days

STUDY DURATION	
 ➤ Subjects will be enrolled for 12 months including screening visit ➤ Follow up for 15 days from enrolment
STUDY POPULATION	
312 Egyptian Patients with pelvi-abdominal infection or started IV antibiotics in post-operative period, for pelvi - abdominal surgeries and/or acute conditions

	
Inclusion Criteria:
 
1. Egyptian male and female patients aged between 18-65

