The simultaneous administration of drugs that induce microsomal liver enzymes, such as Phenytoin or Phenobarbital, may accelerate the elimination of metronidazole while the simultaneous administration of drugs that decrease microsomal liver enzymes activity, such as ceftrimide, may prolong the half-life and decrease plasma clearance of metronidazole.

Ciprofloxacin may increase the effects of caffeine.

Serious and fatal reactions have occurred when Ciprofloxacin was taken in combination with theophylline. These reactions have included cardiac arrest, seizures, status epilepticus, and respiratory failure.

Tendon disorders (tendinitis) have been rarely encountered in some cases related to concomitant use of quinolone with corticosteroids.

9 Research Question & Study Objectives

9.1 Primary Objective:

9.1.1 Primary Safety:

To compare safety of oral Ciprodiazole[®] tablets (Ciprofolxacin/Metronidazole) versus currently used Ciprofloxacin Tablets & Metronidazole tablets in pelvi-abdominal infections, either non-operative or post-operative following IV antibiotics.

9.1.2 Primary Efficacy:

To compare efficacy of oral Ciprodiazole[®] tablets (Ciprofolxacin/Metronidazole) versus currently used Ciprofloxacin Tablets & Metronidazole tablets in pelvi-abdominal infections, either non-operative or post-operative following IV antibiotics

9.2 Secondary Objective:

9.2.1 Secondary Safety:

- Presence of any signs/symptoms of post-operative wound infection such as redness, fever or wound discharge.
- Presence of undesirable effects on total leukocyte count and liver enzymes (SGOT & SGPT)

9.2.2 Secondary Efficacy:

- To compare the complete resolution or improvement of Pelvi-abdominal infection between ciprodiazole[®] versus combined treatment, based on pelvi-abdominal ultrasound and others
- To compare the days for complete healing of post-operative wounds between ciprodiazole[®] versus combined treatment

10 Research Methods

10.1 Study Design:

This is a single center, open Label, controlled, interventional phase IV Study conducted in Menoufia University Hospital in Egypt to compare the safety and efficacy of oral Ciprodiazole[®] tablets (Ciprofloxacin/Metronidazole) versus currently used Ciprofloxacin Tablets & Metronidazole tablets in pelvi-abdominal infection and following IV antibiotics in post-operative period, for pelvi-abdominal surgeries or acute conditions

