10.5.1 Determination of Sample Size

As the primary objective is to assess the safety of oral Ciprodiazole[®] tablets (Ciprofolxacin /Metronidazole) versus currently used Ciprofloxacin Tablets & Metronidazole tablets following IV antibiotics in post-operative period, for pelvi-abdominal surgeries, and based on the previous study "Comparison of Intravenous/Oral Ciprofloxacin Plus Metronidazole Versus Piperacillin / Tazobactam in the Treatment of Complicated Intra-abdominal Infections".^[15] Overall clinical resolution rates were statistically superior for CIP+MET (74%) compared with PIP/TAZO (63%). Mean length of stay was 14 days for CIP1MET and 17 days for PIP/TAZO patients.

So, the following parameters are used to calculate the expected sample of the study:

- Design: non-inferiority
- Sample Size = 312 Subjects (1:1)
- Ciprodiazole Sample Size (Experimental group) = 156 subjects
- Current used regimen Sample Size (Control group) = 156 subjects
- Confidence level 95% (α error = 5%)
- Power = 80%
- Non-Inferiority margin = 2%

10.5.2 Sample Size & Treatment Groups:

Total of 312 Egyptian patients who have pelvi-abdominal infection or started IV antibiotics in post-operative period, for pelvi-abdominal surgeries will be enrolled in the study and randomized, using a computer system, with a ratio of 1:1, into two categories as follows:

1. Group will receive Ciprodiazole[®] tablets; 156 patients
2. Group will receive Ciprofloxacin Tablets & Metronidazole tablets; 156 patients

10.5.3 Randomization:

Subjects will be randomized into the two treatment groups with a balanced ratio of 1:1. Randomization by block Computer-generated randomization lists will be established by Data Management department (DM) of CRO (Nagy Research). The number of patients of the two treatment groups will be balanced (ratio 1:1). (156 Ciprodiazole[®]: 156 Ciprofloxacin Tablets & Metronidazole tablets).

A document describing the procedure of constitution of the randomization lists will be stored confidentially at Nagy Research CRO

Block size: 2, 4

The Randomization list will be done using website:
(<https://www.sealedenvelope.com/simple-randomiser/v1/lists>)

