10.7 Quality Control

10.8.1 Quality Assurance

To ensure uniformity of study procedures across centers, the protocol, case report form, and safety reporting procedures will be reviewed with the investigators and his/her personnel responsible for the conduct of the study. Adherence to the protocol and verification of source data will be achieved through monitoring visits to the center. During the course of study monitoring, the entire study documentation will be checked for completeness and plausibility by the responsible CRA. Once the CRF is completed and signed, the CRA takes the data management copy and the data is entered into the database for analysis. CRFs will be kept in secure locked place or lockers.

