- Presence of any signs/symptoms of post-operative wound infection such as redness, fever or wound discharge will be recorded (in case of post-operative subjects)
- Child-Pugh Score will be calculated for liver impairment and pelvi-abdominal Ultrasound and others will be done
- Lab results will be checked for: (Fasting Blood Sugar (FBS), Total leukocytes count, liver enzymes (SGOT & SGPT), Total Bilirubin and S. Creatinine), and Serum β -HCG for females of child bearing potential only
- The Investigator will keep a log of all subjects, who will sign the ICF. Even if the subject would not pass the screening, his/her signed consent form will be retained

in the Investigator file and will be considered as screening failure. The reason(s) for screen failure will be recorded in the screen failure form in the screening log.

- All data related to screening visit must be reviewed (signed and dated) by the Investigator to ensure that the subject will be eligible for the study, before dispensing the study drug.
- Randomization will be done and subjects will be administered the study products; either Ciprofloxacin® tablets or Ciprofloxacin Tablets & Metronidazole tablets.
- Study products sufficient for the next 7 days will be supplied; either Ciprofloxacin® tablets or Ciprofloxacin Tablets & Metronidazole tablets, and storage conditions will be explained. Study products supplied will be recorded.
- Subjects will be asked to come after 7 days of treatment and bring the empty blisters of medication received, with window of 3 days.

In case of any premature discontinuation of the study, the subject will be, if possible, called in for a last visit. Even if the subject was not able to attend the last visit, the End of Study Form must be completed.

Child-Pugh Score will be recorded, as follows:

The score employs five clinical measures of liver disease. Each measure is scored 1-3, with 3 indicating most severe derangement.^[20]

Table 2: Child-Pugh Score

Measure	1 point	2 points	3 points
Total bilirubin, µmol/l (mg/dl)	<34 (<2)	34-50 (2-3)	>50 (>3)
Serum albumin, g/dl	>3.5	2.8-3.5	<2.8
Prothrombin time, prolongation (secs)	<4.0	4.0-6.0	> 6.0
Ascites	None	Mild	Moderate to Severe
Hepatic encephalopathy	None	Grade I-II (or suppressed with medication)	Grade III-IV (or refractory)

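### Blocks of 2 and 4 in a single-centre open-label trial, with no described concealment of the next assignment, let enrolling staff guess about 72% of assignments correctly

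*Protocol*

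**What the plan says.** - **Design.** The protocol synopsis describes a "Comparative, randomized, Single center, Open label study to compare the safety and efficacy of oral Ciprodiazole 500 mg". Protocol 10.1 agrees: "This is a single center, open Label, controlled, interventional phase IV Study conducted in Menoufia University Hospital in Egypt".
- **Allocation.** Protocol 10.5.3: "Subjects will be randomized into the two treatment groups with a balanced ratio of 1:1". No stratification factor is named. The CRO makes the list: "Randomization by block Computer-generated randomization lists will be established by Data Management department (DM) of CRO". The same section, and SAP 7.3, then print the block sizes as 2 and 4.
- **Confidentiality.** Also in 10.5.3: "A document describing the procedure of constitution of the randomization lists will be stored confidentially at Nagy Research CRO". The block sizes that this document would protect are printed directly below that sentence.
- **Who sees the protocol.** Section 10.8.1: "the protocol, case report form, and safety reporting procedures will be reviewed with the investigators and his/her personnel".
- **Release of an assignment.** Section 12.2 says only that randomisation takes place. Section 12.3.1 (Visit 1) says: "Randomization will be done and subjects will be administered the study products". Neither document describes a central, web, telephone or envelope step.
- **Recognition of the risk.** The limitations section of the protocol states that the randomised open-label design avoids bias from physicians and patients.

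**The concern.** Randomisation protects against selection bias only if the person who decides whom to approach, and when, cannot foresee the next arm. Three features combine here. Treatment is open, so past assignments can be seen. There is one hospital and no strata, so the sequence is easy to follow. The blocks are very small, so the arms return to balance every two or four patients.

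There is room for discretion. The qualifying infections are given as an open-ended list of examples, and other departments may refer patients. If enrolment leaned on the expected arm, prognosis would differ between arms before any drug was taken. The planned chi-square and t-tests are unadjusted and would not correct for that.

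**Working it through.** **The plan's own figure.** The documents give no predictability figure. The only stated number involved is 312 (156 per arm), which here sets the length of the list. It reproduces with rates of 63% and 74%, a 2-point margin, one-sided 5% and 80% power: (1.645 + 0.842)² × (0.74×0.26 + 0.63×0.37) / (0.11 + 0.02)² = 6.183 × 0.4255 / 0.0169 = 155.7, so 156. Whether those are the right inputs is a separate matter.

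**Inputs.** Block sizes 2 and 4 and ratio 1:1 (protocol 10.5.3, SAP 7.3). Assumed: past assignments are visible. Also assumed: each block is a 2 or a 4 with equal probability, since the documents do not give the mix. Ranges are shown below.

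**1. Share guessed correctly.** The rule is to guess the arm that is behind and toss a coin when level. It uses only the running totals. For a block of size 2b the expected number correct is b + (2^(2b)/C(2b,b) − 1)/2.
- Size 2: 1 + (4/2 − 1)/2 = 1.5 of 2, or 75.0%.
- Size 4: 2 + (16/6 − 1)/2 = 2.833 of 4, or 70.8%.
- Equal mix: (1.5 + 2.833)/6 = 72.2%, about 225 of 312, against 156 by chance.

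A simulation of 2,000 lists of 312 gave 72.1%, with 95% of lists between 214 and 237 correct. A guesser who also knew the sizes did no better overall (72.2%).

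**2. How sure the guess is.** The arms are unequal before 1 of 2 assignments in a block of 2 and 2.333 of 4 in a block of 4: 3.333/6 = 55.6%. The lagging arm follows in 1 and 2 of those, so 3/6 = 50.0% of all assignments. An informed guess is therefore right 50.0/55.6 = 90% of the time. Before the other 44.4% the guess is a coin toss.

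**3. Certainty, which does need the sizes.** An imbalance of 2 can occur only inside a block of 4. It arises in 2/6 of such blocks and fixes the next two assignments. If a proportion q of blocks are 2s, the certain share is (2/3)(1 − q)/(4 − 2q).
- q = 0.5: 0.333/3 = 11.1% (simulated 11.1%).
- q = 0.8: 0.133/2.4 = 5.6%.
- q = 0.2: 0.533/3.6 = 14.8%.

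After the first patient of a freshly opened block, staff who know the sizes but not which is running face ½ × 1 + ½ × 2/3 = 5/6, or 83%. Over all unequal but uncertain positions the average is (50.0 − 11.1)/(55.6 − 11.1) = 87.5%.

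**4. Illustrative consequence.** Assume that patients entered when the combined tablet is expected have a resolution rate 5 or 10 points above those entered when control is expected. This shift has no source in the documents.
- Bias = shift × (2 × 0.722 − 1) = shift × 0.444, so 2.2 or 4.4 points.
- With a base rate of 74% and 156 per arm, the standard error is √(2 × 0.74 × 0.26/156) = 4.97 points.
- At 2.2 points (0.447 SE), the two-sided 5% test rejects with probability 0.065 + 0.008, about 7%. At 4.4 points (0.895 SE): 0.143 + 0.002, about 14-15%.
- With 78 per arm (illustrative), the standard error is 7.02 points and the 10-point case gives about 10%.

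**5. Alternatives.**
- Blocks of 8, 10 and 12: (5.329 + 6.532 + 7.717)/30 = 65% correct, about 1% certain.
- Big-stick rule with maximum imbalance 8: long-run forced share 1/16, about 6%; correct guesses 0.5 + 0.0625/2, about 53%.
- Under the 10-point illustration the residual bias is 3.1 points with the larger blocks and 0.6 with the big stick.

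**The case against.** **Printing the sizes.** A reader might infer that staff can guess because both documents print the block sizes. They cannot be said to: the 72% comes from small blocks and visible past assignments, and deleting the printed sizes leaves it unchanged. Printing adds the certain cases.

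**Guessing is not knowing.** A reader might also infer that the next assignment is fixed after one patient. That is true of a block of 2 on the list, but not of what staff know, because the running size is hidden. Only about one assignment in nine is certain.

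**Steering is hypothetical.** Nothing in the documents shows it, and the prognosis shifts are invented for scale. They also suppose that staff act on every guess throughout. Efficacy is analysed per protocol only, and wound healing concerns only post-operative patients, so real denominators and the inflation would be smaller. It is tempting to quote an inflated false non-inferiority rate, but the plan contains no non-inferiority test, only chi-square comparisons.

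**Partial safeguards.** Consent and eligibility review come before randomisation, the investigator must sign off screening data before dispensing, and the CRO makes the list. That one group sees every past assignment is an inference from a single site and open treatment.

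All of this limits the size of the point. It does not remove it: the safeguards act after someone has decided whom to approach and when, and no described step hides the next arm at that moment.

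**Conclusion.** The point stands as a weakness in allocation concealment that should be corrected. With past assignments visible, about 72% of assignments can be guessed (70.8% to 75.0% over all mixes of 2s and 4s). About 11% are certain to someone who knows the sizes (5.6% to 14.8% as the share of 2-blocks runs from 80% to 20%). These figures rest on the stated block sizes and on visibility, which the open single-site design makes likely.

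The bias and error-rate figures are illustrations under an assumed shift and are not estimates for this trial. The documents support an unclosed opportunity for selection. They do not support a claim that selection will occur or that most assignments are known in advance.

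**What to change.** In order of importance, in protocol 10.5.3, 12.2 and 12.3.1 and SAP 7.3:

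1. State that the CRO releases each assignment centrally, one at a time, only after consent and eligibility are recorded and the patient is irrevocably registered.
2. Drop blocks of 2 and 4. Preferably use a big-stick rule with maximum imbalance 8. Larger mixed blocks such as 8, 10 and 12 are the minimum, and only a partial remedy at 65% correct guesses.
3. Remove the sizes from both documents and keep them, or the parameters of the replacement rule, in the CRO's confidential document. Alone, this would not lower the 72%.

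The cost is a new list, a few lines of text and a release procedure at the CRO. The arms may differ by a few patients. At 160 v 152 the relative information is 4 × 160 × 152/312² = 0.9993, a loss of under 0.1%. Sample size, visits and treatment are unaffected.

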In this study, we compare the safety and efficacy of oral Ciprofloxacin 500 mg® (Ciprofloxacin /Metronidazole) versus currently used Ciprofloxacin Tablets & Metronidazole tablets in pelvi-abdominal infections and/or following IV antibiotics in post-operative period, for pelvi-abdominal surgeries or acute conditions

7.2 Correlative Studies:

The results of a randomized trial comparing sequential Intravenous (IV) / oral treatment with Ciprofloxacin plus Metronidazole to Imipenem/ Cilastatin for IAIs showed that Ciprofloxacin plus Metronidazole were found to be effective for the treatment of serious and complicated IAIs. In addition, sequential IV/ oral therapy with Ciprofloxacin plus Metronidazole was efficacious in patients able to tolerate oral intake.^[14]

The comparison study of IV / oral Ciprofloxacin plus Metronidazole versus Piperacillin / Tazobactam in the treatment of complicated IAIs proved that initial administration of IV Ciprofloxacin plus Metronidazole followed by oral Ciprofloxacin plus Metronidazole therapy is clinically more effective than IV Piperacillin/Tazobactam for the treatment of patients with complicated IAIs.^[15]

A meta-analysis of comparative trials of Ciprofloxacin/metronidazole versus β – lactam in treatment of IAIs suggested that the ciprofloxacin/metronidazole combination may be superior to β – lactam-based therapeutic regimens in the treatment of IAIs with regard to cure of infections, although no difference in mortality was found.^[16]

8 Treatment:

The treatment will be prescribed in the usual manner in accordance with the terms of the local marketing authorization with regards to dose, population and indication.

8.1 Ciprodiazole® Tablets:

Each film coated tablet of Ciprodiazole® consists of Ciprofloxacin hydrochloride 500 mg, Metronidazole 500 mg, and excipients; pregelatinized starch, sodium starch glycolate, P.V.P K 30, lactose monohydrate 200 mesh, sodium lauryl sulphate, magnesium stearate, and wincoat green. It is indicated for Pelvi-abdominal infections caused by *E. coli*, *Pseudomonas aeruginosa*, *Proteus mirabilis*, *Klebsiella pneumonia*, or *Bacteroides fragilis* and diverticulitis. Ciprodiazole® is manufactured by Minapharm under Marketing Authorization Number: 26357/2009, dated 01/10/2009

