After oral administration, Ciprofloxacin is well absorbed from the abdominal tract. Oral bioavailability is approximately 70 %^[17] and a peak plasma concentration of about 2.5 mcg per ml is achieved after 1 to 2 hours after a dose of 500 mg by mouth. Metronidazole is rapidly absorbed, 80 % is absorbed in one hour. The peak concentration is achieved after 1 to 2 hours after the oral administration. Metronidazole passes the placenta and the maternal milk. The essential excretion is through the liver and the bile. They are absorbed readily and almost completely from the gastrointestinal tract. Serum concentrations reach their peak within one hour of oral ingestion.

Ciprodiazole is contraindicated in the following conditions:

- Hypersensitivity to ciprofloxacin or other antibiotics of Quinolones group such as Ofloxacin, Norfloxacin, Trovofloxacin, and Ofloxacin.
- Hypersensitivity to the metronidazole or other nitroimidazole derivatives
- Children and adolescents below 16 years.
- Epilepsy or other seizure disorders.

- Patients with Glucose-6-Phosphate Dehydrogenase (G6PD) enzyme deficiency.

Sponsor will provide the study treatment for the patients' whole duration according to regulation of Local Health Authorities involved in the product supply since the drug is being used according to the approved marketing label.

The investigator and the research team must evaluate all adverse events and laboratory abnormalities during the study.

A drug-related toxicity or laboratory value outside of the reference range; that is judged by the investigator as having a "reasonable possibility" of being related to the study drug; will be considered as an adverse event.

Drug-Toxicity is deemed "clinically significant" based on the medical judgment of the investigator. Laboratory abnormalities will be managed as deemed clinically appropriate by the investigator until resolved.

The investigator should ensure that any study drug interruptions or dose modifications and associated adverse events are promptly entered into the medical records.

8.2 Ciprofloxacin Hydrochloride:

Ciprofloxacin is a synthetic broad spectrum fluoroquinolone antibiotic. It acts by inhibiting DNA gyrase, which is essential in the reproduction of bacterial DNA. This agent is more active against Gram-negative bacteria than Gram-positive bacteria and aerobic organisms commonly encountered in pelvi-abdominal infections. ^[18 - 19]

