Ciprofloxacin is indicated for the treatment of the following infections caused by susceptible organisms: urinary tract infections, acute uncomplicated cystitis, chronic bacterial prostatitis, lower respiratory tract infections, acute sinusitis, skin and skin structure infections, bone and joint infections, complicated Pelvi-abdominal infections (used in combination with metronidazole)^[1, 4], infectious diarrhea, typhoid fever (enteric fever), uncomplicated cervical and urethral gonorrhea, inhalational anthrax (post-exposure), and to prevent infections occurring after operations.

Ciprofloxacin is well absorbed from the abdominal tract. Oral bioavailability is approximately 70% ^[17] and a peak plasma concentration of about 2.5 mcg per ml is achieved after 1 to 2 hours after a dose of 500 mg by mouth. The serum elimination half-life in subjects with normal renal function is approximately 4 hours. Approximately 40 to 50% of an orally administered dose is excreted in the urine as unchanged drug. ^[18]

Ciprofloxacin is contraindicated in subjects with a history of hypersensitivity to ciprofloxacin or any member of the fluoroquinolone class of antimicrobial agents. The most frequently reported drug related events, from clinical trials for all indications of ciprofloxacin therapy were nausea, diarrhea, liver function tests abnormality, vomiting, and rash.

8.3 Metronidazole:

Metronidazole belongs to a group of medicines called anti-infective agents. It may be used to treat infections, caused by bacteria of the blood, brain, bone, lung, stomach lining and pelvic area, following childbirth or an operation. Also, it is used to treat urinary or genital infections caused by Trichomonas Vaginalis, Gardnerella Vaginalis, Giardia lamblia and Entamoeba histolytica, gum and teeth infections, infected leg ulcers or pressure sores, stomach ulcers caused by Helicobacter pylori or to prevent infections occurring after operations.

Metronidazole is a prodrug. Unionized metronidazole is selective for anaerobic bacteria due to their ability to reduce metronidazole to its active form. This reduced metronidazole then covalently binds to DNA, disrupt its helical structure, inhibiting bacterial nucleic acid synthesis and resulting in bacterial cell death.

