After oral administration, Metronidazole is rapidly absorbed, 80 % is absorbed in one hour. The peak concentration is achieved after 1 to 2 hours after the oral administration. Metronidazole passes the placenta and the maternal milk. The serum elimination half-life in subjects is 8 hours. The essential excretion is through the liver and the bile.

The most common side effects include: allergic reactions such as skin rash, swelling of the face, lips, tongue or throat, fever or difficulty in breathing.

Metronidazole is contraindicated in case of Hypersensitivity to Metronidazole and First trimester of pregnancy, while it should be administered with caution to patients with the following conditions:

- Convulsive seizures and peripheral neuropathy
- Patients with active neurological disorders
- Decreased Neutrophils or a history of blood dyscrasias
- Prolonged QT interval on ECG
- Severe liver disease

8.4 Dosage & Administration:

8.4.1 Ciprofloxacin[®] Tablets:

The recommended dosage of ciprofloxacin[®] is 1 tablet every 12 hours for a duration not exceeding 15 days, according to the investigator's decision. The tablet should be swallowed with plenty of water.

8.4.2 Ciprofloxacin[®] Tablets:

The recommended dosage of Ciprofloxacin tablets is 500 mg every 12 hours for 7 to 14 days, according to the investigator's decision. Tablets should be swallowed with plenty of fluid, during or after meals. It is contraindicated to be taken with dairy products such as milk or yoghurt or with fortified fruit juices (e.g. calcium-fortified orange juice).

The usual dose of Ciprofloxacin should be modified in patients with severe renal impairment, as the following table of the dosage guidelines, according to the Creatinine Clearance (CrCl):

CrCl (mL/min)	Dose
> 50	Usual Dosage
30 – 50	250 – 500 mg every 12 h
5 – 29	250 – 500 mg every 18 h
Patients on hemodialysis or Peritoneal dialysis	250 – 500 mg every 24 h (after dialysis)

8.4.3 Metronidazole[®] Tablets:

Tablets should be swallowed with plenty of water, during or after meals. The recommended dose is 7.5 mg/kg every 6 hours (approx. 500 mg for a 70-kg adult every 6 hours). A maximum of 4 g should not be exceeded during a 24-hour period for 7 to 10 days, according to the investigator's decision.

For patients with severe renal impairment ($\text{CrCl} < 30$), the dose of Metronidazole[®] Tablets should be reduced by 50%

8.5 8.5 Precautions:

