Fluoroquinolones are contraindicated with patients with known history of myasthenia gravis, because they have neuromuscular blocking activity and may exacerbate muscle weakness.

The overdose may lead to loss of appetite, diarrhea, metallic taste, headache, dizziness, insomnia or drowsiness.

The following is a list of possible side effects that may occur, rarely, from the use of Ciprofloxacin[®] tablets:

- Allergic reactions such as rash, itching, and swelling of the mouth, face, lips, or tongue
- Nausea, headache, anorexia, diarrhea, unpleasant metallic taste, stomach cramps pain, vomiting, fainting, and fever.
- Reversible neutropenia (leukopenia), and blood dyscrasias.
- Dysuria, darkening of urine, cystitis, bloody stools, abdominal and vaginal yeast infection.
- Tendon inflammation and damage.
- Irregular heartbeat and loss of consciousness.
- Mood or mental changes such as anxiety, confusion, depression, and sleeplessness.
- Convulsive seizures and peripheral neuropathy tremors.
- Jaundice.

8.5.1 Storage and Drug Accountability:

Study drugs are to be stored at room temperature up to 30 degrees C (86 degrees F). Keep them in the original containers. Store away from heat, moisture, and light. Do not store in the bathroom. Keep them out of the reach of children and away from pets.

All empty, partially used, and unused blisters will be retained by the Investigator (at room temperature) until they are returned to the pharmacist and to be checked by monitor.

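### Five contraindications that protocol section 8 states for the study drugs appear in no eligibility criterion

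*Protocol*

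**What the plan says.** Protocol 8.1 lists the conditions in which Ciprodiazole is contraindicated. Besides age below 16, the list has four entries:

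- "Hypersensitivity to ciprofloxacin or other antibiotics of Quinolones group such as Ofloxacin, Norfloxacin, Trovofloxacin, and Ofloxacin"
- "Hypersensitivity to the metronidazole or other nitroimidazole derivatives"
- "Epilepsy or other seizure disorders"
- "Patients with Glucose-6-Phosphate Dehydrogenase (G6PD) enzyme deficiency"

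Protocol 8.2 repeats the class-level allergy for the single agent: "Ciprofloxacin is contraindicated in subjects with a history of hypersensitivity to ciprofloxacin or any member of the fluoroquinolone class of antimicrobial agents". Protocol 8.5 adds a fifth condition: "Fluoroquinolones are contraindicated with patients with known history of myasthenia gravis".

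The exclusion criteria appear three times, in the synopsis, in protocol 10.2.2 and in SAP 3.2, with ten items each. Exclusion 1 covers allergy to the active ingredients of the study treatments and goes no further. Exclusion 5a covers patients who need enzyme-inducing drugs, with phenytoin and phenobarbital as examples. Protocol 12.2 has each patient screened against the listed inclusion and exclusion criteria, after which randomisation follows.

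**The concern.** The product section and the eligibility section of one protocol do not agree on who may receive the drug. A patient with epilepsy treated with something other than an enzyme inducer, or with known myasthenia gravis, or with a past reaction to ofloxacin, breaches none of the ten exclusions. Screening against the list as written would pass that patient. Randomisation is 1:1, so any patient who passes may be given Ciprodiazole.

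What is at stake is avoidable exposure of participants in a trial that has safety as a primary objective. It is not a matter of power, error rate or estimation.

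**Working it through.** The plan states no figure on this point, so the check is a comparison of texts. I took every statement in protocol section 8 that uses the word contraindicated for a patient condition or a co-medication, split compound entries, removed repeats, and looked for each in protocol 10.2.1 and 10.2.2, the synopsis, and SAP 3.1 and 3.2.

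| # | Contraindication | Stated in | Carried into |
|---|---|---|---|
| 1 | Ciprofloxacin hypersensitivity | 8.1, 8.2 | Exclusion 1 |
| 2 | Hypersensitivity to other quinolones | 8.1, 8.2 | none |
| 3 | Metronidazole hypersensitivity | 8.1, 8.3 | Exclusion 1 |
| 4 | Hypersensitivity to other nitroimidazoles | 8.1 | none |
| 5 | Age below 16 | 8.1 | Inclusion 1 (18-65) |
| 6 | Seizure disorders | 8.1 | none |
| 7 | G6PD deficiency | 8.1 | none |
| 8 | First-trimester pregnancy | 8.3 | Exclusion 10 |
| 9 | Myasthenia gravis | 8.5 | none |
| 10 | Tizanidine | 8.8 | Exclusion 5f |
| 11 | Antacid, calcium, iron and zinc products | 8.8 | Exclusion 5e |

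**Count.** Section 8.1 gives 7, 8.3 adds 1, 8.5 adds 1 and 8.8 adds 2: 7 + 1 + 1 + 2 = 11. Carried: items 1, 3, 5, 8, 10 and 11 = 6. Not carried: 11 - 6 = 5, of which four come from 8.1 and one from 8.5.

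**Near misses.** Exclusion 5a removes only those seizure patients who need an enzyme inducer. Exclusion 5c mentions seizures only as a reaction to theophylline given with ciprofloxacin. Neither excludes seizure disorder as such.

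**Sensitivity of the count.**
- Section 8.4.2 also calls dairy and fortified juice contraindicated with ciprofloxacin tablets. I left this out because it concerns how to take the tablet. With it the total is 12, and the number not covered is 5 or 6, depending on whether exclusion 5e is read to include dairy.
- If each 8.1 bullet is kept whole, there are 9 entries: 4 covered, 2 partly covered (the two allergy bullets) and 3 wholly absent.
- The same five gaps remain under each way of counting.

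**Exposure by arm.** The combination tablet "consists of Ciprofloxacin hydrochloride 500 mg, Metronidazole 500 mg, and excipients", and its dose in 8.4.1 "is 1 tablet every 12 hours for a duration not exceeding 15 days". The control doses are in 8.4.2 and 8.4.3.

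- Ciprofloxacin: 2 x 500 = 1000 mg a day in each arm.
- Metronidazole, Ciprodiazole arm: 2 x 500 = 1000 mg a day.
- Metronidazole, control arm, 70-kg adult: 4 x about 500 = about 2000 mg a day (7.5 x 70 x 4 = 2100 mg before rounding).

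Neither arm spares the patient either drug.

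**The case against.** The strongest reply is that section 8 is itself part of the protocol. It ties prescribing to the local marketing authorization. Section 10.1 requires care to follow the protocol and local standards, 10.2.1 makes a patient who meets the criteria only a candidate for enrolment, and 12.3.1 has the investigator review and sign the screening data before dispensing. Under 10.2.3 the investigator may also withdraw a participant for any reason. On this reading, giving Ciprodiazole to a patient with known epilepsy already contradicts the protocol, and what is missing is a copy of section 8 in the criteria list.

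Part of this stands: the safeguards are real and lower the risk. None of them is an eligibility criterion, however, and the sign-off certifies eligibility against a list that omits the five conditions. The protocol turned its other six contraindications into criteria and gives no reason for leaving these out.

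A second reply concerns the control arm. Seizure disorders, G6PD deficiency and allergy to other nitroimidazoles are stated as contraindications only for Ciprodiazole, and 8.3 lists convulsive seizures for metronidazole only as a reason for caution. That is correct, so for those three the conflict in the text lies with the Ciprodiazole arm. Eligibility is settled before allocation, though, so the criteria must suit both arms.

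A third reply is that the practical gain is a checklist prompt. That is fair as a description, but the prompt costs almost nothing.

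**Conclusion.** The concern holds. Five of the 11 contraindications stated in section 8 are in no eligibility criterion: seizure disorders, G6PD deficiency, myasthenia gravis, allergy to other quinolones and allergy to other nitroimidazoles. Applied as written, the criteria admit patients whom the protocol's own product section says should not receive the drug.

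The total of 11 rests on splitting the two allergy bullets and leaving out the dairy and juice instruction; the five gaps do not depend on either choice. The number of patients affected cannot be derived from the documents, and the sample size, power and analyses are unaffected. The point should be fixed because it bears on participant safety and the remedy is small.

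**What to change.** Amend the synopsis, protocol 10.2.2 and SAP 3.2 in the same words:

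1. Add an exclusion for a history of epilepsy or any other seizure disorder.
2. Add an exclusion for known G6PD deficiency, established by history, with no test.
3. Add an exclusion for known myasthenia gravis.
4. Widen exclusion 1 to hypersensitivity to any quinolone or any nitroimidazole.

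Apply all four to every patient before randomisation. The metronidazole caution in 8.3 can stay as it is, since it concerns that drug alone and the new exclusion meets the stricter Ciprodiazole contraindication.

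The cost is a wording amendment in three places. The answers come from the medical history already scheduled at visit 1, so no test or visit is added. A few patients become ineligible, in a number the documents do not allow one to estimate, and undiagnosed G6PD deficiency will still go undetected.
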